6.5. BRAIN MRI AND PET IMAGING PROTOCOLS

MRI protocols are performed in 50-70 minutes and will be conducted at The Center for Systems Imaging (CSI). The MRI protocol includes:

(*i*) *Structural MRI and WMH*: High-resolution anatomical images will be acquired using a 3D-Fast Spoiled Gradient Recalled Echo (FSPGR) Sequence. WMH regions will be identified by a 3D T2 Fluid Attenuated Inversion Recovery (FLAIR) Fast Spin Echo sequence.

(*ii*) ASL-MRI: ASL images will be acquired using a custom 3D stack of interleaved spirals fast spin echo sequence and will be averaged in order to improve the signal-to-noise ratio. In addition to resting perfusion, scans will be taken during normocapnia (2 minute scan) and hypercapnia (breathe a mixture of 8% CO2 for 2 minute scan). The following metrics will be calculated: resting perfusion, Vasoreactivity (VR)=slope of the regression between cerebral perfusion and end-tidal CO2, in ml/100g/min per mm of Hg during normal and hypercapnia.

(iii) Diffusion tensor imaging: DTI is highly sensitive to detect structural changes over a short time, less than 1 year, as compared to traditional MRI.⁶⁹

(iv) Resting state functional MRI (rs-fMRI): Resting state fMRI will be used to assess "functional connectivity" between brain regions.⁷⁰ Functional connectivity has a key role in important complex cognitive processes.⁷⁰ It

focuses on spontaneous, rather than task-induced, low frequency (<0.1 Hz) fluctuations in the blood oxygenation level-dependent (BOLD) signals.

(v) In-vivo A8- and Tau PET imaging: This will be performed on the original sample (n=72). Participants will be selected consecutively for the original study until up to a total sample of 72 complete the PET studies (36 per group). In-vivo amyloid imaging will be conducted using N-methyl-[¹¹C] 2-(4'-methylaminophenyl)-6-hydroxybenzothiazole also termed [¹¹C] Pittsburgh Compound B (PiB),⁷¹ following ADNI protocol.⁷² PET images (20 minutes; 4×5 minute frames) will be acquired approximately 50 minutes after intravenous administration of 15±1.5 mCi of [¹¹C] PiB. Images will be analyzed as recently recommended.⁷³ In certain cases (see eligibility section) PiB Pet can be performed at screening to determine amyloid positivity. *In-vivo Tau-PET imaging* will be conducted using ¹⁸F-labeled benzimidazole pyrimidine, 7-(6-[¹⁸F]fluoropyridin-3-yl)-5H-pyrido[4,3-b]indole ([¹⁸F]T807) which has been shown to have selectively high affinity to Tau; and T807 PET scans are now available to measure in-vivo Tau content in patients with MCI and AD.⁷⁴⁻⁷⁸

6.6. VASCULAR MEASURES

Arterial stiffness and microvascular function: Indices of arterial stiffness and wave reflections will be estimated in the supine position using the Sphygmocor device (Atcor Medical, Australia), which records sequential highquality pressure waveforms at peripheral pulse sites using a high-fidelity tonometer. Pulse-wave velocity (PWV) measured between carotid and femoral arteries is a regional assessment of aortic stiffness and is the gold standard index of arterial stiffness. Digital pulse amplitude tonometry (PAT) will be used to measure pulse volume amplitude (PVA) in the tip of the index finger, with participants resting in the supine position in a quiet, temperature-controlled environment and during reactive hyperemia, which will be elicited by the release of an upper arm blood pressure cuff inflated to supra-systolic pressure for 5 minutes. The Endo-PAT (Itamar-Medical, Israel) will be used to measure PAT. The reactive hyperemia index (RHI) is a marker of endothelial function.

Blood pressure and Ultrasound: A brachial BP will be measured twice while seated and after 1 and 3 minutes standing according to the AHA guidelines.⁹⁴ High-resolution B-mode ultrasound of the right common carotid artery using a 7.5-MHz linear-array will be performed to measure carotid intima-media thickness (IMT).⁹⁵

6.7. PROTEOMICS AND INFLAMMATORY MARKERS

We will conduct proteomic and metabolomics studies of the CSF and blood samples (screening/baseline & 12 months) at the Emory Neuroscience NINDS Core Facilities (ENNCF) and the Emory Metabolomics core. We will use a targeted proteomic approach with selected reaction monitoring (SRM).⁸² Our set of proteins in the targeted proteomic analysis are enriched with the inflammatory/oxidative stress pathways: adhesion molecule,⁸³ cytokines (see Hu et al⁸⁴ for full list), oxidative stress (F2-isoprostanes),^{85,86} and BBB integrity proteins (astrocytic protein S100 β , neuron-specific enolase (NSE) and RAGE).⁸⁷⁻⁸⁹

6.8. RENIN ANGIOTENSIN SYSTEM ACTIVITY

RAS activity will be assessed using a comprehensive analysis of different angiotensin peptides measured simultaneously in a single sample by a highly selective and sensitive mass spectrometry method described previously.⁹⁰ We will use this to assess the degree of blockade of AT1 and activation of AT2.

6.9. BLOOD CHEMISTRIES, BLOOD COUNT, AND APO-E

Blood will be drawn at various visits. Please refer to the table for specific tests done at each visit.

6.10. BLOOD AND CSF BANKING

We will collect blood and CSF samples for future research. Vials containing blood samples will be labeled with subject ID numbers, name of the study, date collected and barcoded and stored at the cryogenic storage facility

until time of processing. The label will include the study name, study visit number, contents of each collection vial, and the date of collection. The samples will be kept until the samples are exhausted. Future study results obtained from these samples may not be reported to subjects. For those who agree to have their retina scanned, an additional (10 cc) of blood will be drawn during or close to the retinal scan visit.

6.11. RETINAL AMYLOID SCAN

We will perform retinal imaging on the study subjects to test the utility and suitability of retina imaging for detecting AD markers. This is a non-invasive procedure that requires dilation of the eyes and obtaining photographs of the retina. Retinal scans can be done during or after the participant has completed the study. Those already completed will be re-contacted for this procedure.

6.12. SCHEDULE OF EVALUATIONS

6.12.1. SCREENING

Individuals who express an interest will have a 2-tier screening process. Individuals meeting criteria of a clinical diagnosis of MCI will undergo further screening. Those who are eligible, i.e. have MCI will undergo a clinical evaluation (clinician interview, review of prior imaging, review of prior CSF analysis). If no clinical data is available to confirm AD biomarkers in the CSF within the last 24 months, an LP will be performed. This will be scheduled on a separate visit or on the same day if safety labs are available on that day.

6.12.2. ENROLLMENT, BASELINE, AND FOLLOW-UP

Once eligible, baseline evaluation will be completed. An LP will be done if not done during the screening visit. Once baseline data are collected, participants will be randomized into candesartan or placebo and seen every two weeks where study dose will be increased to 16 mg and 32 mg until MDT is achieved. They will be seen afterwards every three months until the study ends. All visits will have a +/- three week window except during medication escalation visits where the window will be +/- 5 days. An optional modified phone/virtual visit will be completed as needed for any visit to collect data that can be reasonably collected by phone. This change is in response to the COVID-19 stay home orders and in-person research activities will resume when normal business operations resume. Study procedures are shown in the **Table above**.

7. SAFETY ASSESSMENTS

7.1. SPECIFICATION OF SAFETY PARAMETERS

(i) The following safety parameters are related to the use of Candesartan: rash, dizziness, cough, weakness, fatigue, headaches, lower extremity edema, constipation, back pain, sore throat, upper respiratory tract infection, rhinitis, pharyngitis and hoarseness. Angioedema, renal failure (Cr>2.5), hyperkalemia (K>5.9 meq/dl), and fainting are also potential complications of candesartan.

(ii) The following safety parameters are related to the conduct of the study procedures: Neuropsychological assessment may be accompanied by anxiety, frustration and overall fatigue. The attachment and removal of a blood pressure cuff, cuffs for venous occlusion, and ultrasound probe on the neck may cause mild discomfort. Brain imaging requires the participant to stay still and lie down for 50-70 minutes, which may cause boredom and minimal reversible back pain. Because of the closed space and noise, undergoing an MRI may be associated with anxiety or panic reactions. We will ask participants to breathe via a mask air richer in CO2 than normal atmospheric air (5-8%) during the brain MRI procedure. The reported potential side effects may include a feeling of dizziness, faintness, or anxiety during CO2 inhalation. CO2 administration will be promptly terminated if any of the aforementioned conditions occur. The vascular ultrasound is safe and only mildly uncomfortable due to

tightness in the arm when the cuff is inflated. We will use ultrasound to painlessly bounce sound beams off of the carotid artery using a pencil-like sensor.

(iii) The following safety parameters are related to the LP procedure: The most common complication of a lumbar puncture is post-LP headache. We use a smaller 24-gauge Sprotte spinal needle. All subjects will be counseled on the signs and symptoms of post-LP headaches and given information on management (acetaminophen, caffeine, rest). Bacterial meningitis and a CSF leak are very rare complications of lumbar punctures. A blood patch is rarely needed to heal CSF leaks. All subjects will be instructed to promptly contact us if the headache persists beyond 3 days and if a blood patch is required, the cost of the patch will be covered by the funds supporting this project.

(iv) Potential risks of the study PET imaging are as follows: There may be discomfort, bruising, bleeding or infection at the site of the intravenous puncture. The radiation exposure is within limits acceptable to the Emory University Radioactive Drug Research Committee. Systemic toxic effects attributable to single dose T807 or PiB have not been encountered. Both ligands are rapidly cleared from the plasma and their binding to their target is reversible. Toxicity remains a possibility and patients will be monitored for such events during the scan and at follow-up.

(v) Potential risks of the retinal amyloid scan are as follows: Adverse reactions to dilation of the eyes may include discomfort, irritation, or other reactions similar to pupillary dilation experienced during a visit to the eye doctor. Increased sensitivity to bright lights may be experienced. We will provide disposable sunglasses to counteract these effects. Participants will be monitored for adverse effects.

7.2. METHODS FOR ASSESSING AND RECORDING SAFETY PARAMETERS

During the course of the study, any problem reported by the participants will be recorded in the participant's chart (adverse event log), along with the start and stop dates. The problem may be related to the research participation or the drug used in the study (drug reaction). All Adverse events will be rated on the following characteristics:

(i) Serious (YES/NO): A serious adverse event (SAE) is defined using the Code of Federal Regulations Title 21 definition as any event that results in any of the following outcomes: Death, a life-threatening adverse event, inpatient hospitalization or prolongation of existing hospitalization, a persistent or significant incapacity or substantial disruption of the ability to conduct normal life functions, or a congenital anomaly/birth defect.

(ii) Related to the research: All adverse events will be judged regarding their relationship to the research participation or the study drug as related, possibly related, probably related, unrelated, or unknown.

(iii) Severity: The severity of the AE will be rated on the following scale mild, moderate, severe, life-threatening, or death.

(iv) Anticipated or unanticipated: We use the Emory IRB definition of an unanticipated event as any event that is "unexpected, not described in the study documents, or if described before, it is now presenting with increased severity, duration, or frequency".

7.3. REPORTING ADVERSE EVENTS AND DEATH

Principal Investigators shall immediately (within 24 hours of the event) report to the Radioactive Drug Research Committee all adverse effects associated with the use of the radioactive drug in the research study. All adverse reactions probably attributable to the use of the radioactive drug in the research study shall be immediately reported (within 24 hours of receiving the initial report) by the RDRC to the Food and Drug Administration, Center for Drug Evaluation and Research. All other adverse events will be assessed for the need for prompt reporting. We follow the guidelines set-forth by the Emory IRB for reporting AE's. Any event that fulfills the following criteria being unanticipated (as defined in section 7.2), probably or possibly related to study participation (drug effect or as a consequence of a study procedure), and involving risk for participants or others is considered an unanticipated problem and will be reported to the Emory IRB within 10 days. If an event could be explained by the underlying medical condition, it is not considered related and hence not reportable. Any SAE as defined in **section 7.2** that does not fit all the criteria of being an unanticipated problem will be reported during continuing review. Deaths of participants during the study will be promptly reported to the IRB if related to study participation and reported during continuing if they are not related to study participation. A yearly summary of AE/SAE/Deaths will be presented to the DSMB by the study biostatistician.

7.4. FOLLOW-UP FOR ADVERSE EVENTS

All AE/SAE's will be recorded in the participant chart with start/stop date. The study physician may perform additional evaluations, visits, phone communication, repeat blood testing, or refer to the emergency room or the participant healthcare provider for medical care if necessary. If the event results in intervention discontinuation and/or study withdrawal, the participant will be followed for 2 months post-withdrawal with a monthly phone call. They will also be invited to perform the final visit evaluation including all study procedures planned for that visit if the participant has been in the study more than 5 month post baseline evaluation.

Follow-up on reported symptoms of hypotension or a BP<100/40 mm Hq: When a subject notifies the study team that they have either symptoms suggestive of hypotension (dizziness, weakness, near syncope, or syncope) or that their blood pressure is less than 100/40 mm Hg, the study physician will review the incident and determine if the subject is safe to continue in the study. The physician may discontinue the study medication immediately, elect to lower the dose of the study medication, ask subject to present to the study center for a safety evaluation, and/or monitor the subject blood pressure. The subject may continue in the study if blood pressure is >100/40 mm Hg on the lower dose of the study medication and had resolution of symptoms. In those on 16 mg and 32 mg, the doses will be decreased to the next lower dose. Those on 8 mg of candesartan, a trial of every other day 8 mg of candesartan will be attempted prior to discontinuation.

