1. STUDY OBJECTIVES

Our *Primary objective* is to determine the safety and dose-response of target engagement for treatment with escalating doses of candesartan in those with mild cognitive impairment (MCI) and Alzheimer's disease (AD).

Our *secondary objectives* are to assess the efficacy of 1 year treatment of candesartan on biomarkers of vascular function, neurodegeneration, and neuro-inflammation; to assess the efficacy of 1 year treatment with candesartan on amyloid imaging; and to estimate the effect size of Candesartan on cognitive and functional measures in MCI and AD.

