5. STUDY INTERVENTIONS

5.1. INTERVENTIONS, ADMINISTRATION, AND DURATION

Participants will be randomized to either candesartan or placebo in a 1:1 fashion. All participants will be initiated on 8 mg. The dose will be increased in 2 week increments to 16 mg and 32 mg as long as: SBP>110 mm Hg, DBP>40 mm Hg and participant reports no symptoms of hypotension (dizziness or weakness). The highest achievable dose will be the Maximal Tolerated Dose (MDT) and will be prescribed for the duration of the study. The cut-off of 110 mm Hg for SBP is based on the evidence that a decrease of ≤5 mm Hg in SBP is expected in non-hypertensive individuals. Hence, a cutoff of 110 mm Hg in SBP decreases the risk of developing hypotension (defined as <100 mm Hg in SBP). Treatment will be provided in similar capsules format to be taken once a day orally. Investigators, study personnel and participants will be blinded for drug assignment. Participants will be treated for 1 year.

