8. INTERVENTION DISCONTINUATION

A subject may choose to withdraw from the study for any reason. The investigators may also request that the subject withdraw from the study, for safety or other reasons. The criteria for discontinuing a subject's participation include:

(1) the subject's request,

(2) adverse events that requires un-blinding or necessitate stopping the study drugs,

(3) persistent (>2 episodes on 2 separate days) of symptomatic hypotension or a blood pressure <100/40 mm Hg on 2 separate occasions despite adjusting study medication to the lowest dose (see section on follow-up on AE 7.4).(4) new clinically evident stroke or myocardial infarction or other event that limits ability to complete the study procedures

(4) inability to participate due to relocation or other personal reasons,

(5) renal failure (increase in serum Creatinine above 2.5 mg/dl) or hyperkalemia (greater than 5.9 meq)

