9. STATISTICAL CONSIDERATIONS

9.1. GENERAL DESIGN

The study is a 2-arm double-blinded RCT. The statistical analysis will follow the intention-to-treat approach. Intention-to-treat (ITT) and per-protocol analyses will be performed.

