9.3. DATA ANALYSIS

 Table 2 provides a list of main outcomes.

Table 2: Independent, main outcome and other variables to be used in the analyses		
Independent:	Group (Candesartan vs placebo)	
Safety outcome:	hypotensive episodes, symptoms (dizziness, weakness, cough) , creatinine >2.5 mg/dl , K>5.9 mEq/dl, number of discontinuations of candesartan, AE, SAE, Deaths	
CSF outcomes:	CSF tau, inflammatory proteins	
Vascular outcomes:	PWV, augmentation index	
Imaging outcomes:	Perfusion, hippocampal volume, vasoreactivity, Global SUVR (PiB and T807)	
Cognitive outcomes:	CDR, EXAMINER, HVLT, TMT (B and B-A)	

Baseline characteristics including demographic, APOe, social and cognitive measures will be compared between the 2 groups to assess randomization fidelity. The list of the main variables is shown in Table 3. We will compare the change in our outcomes over the study period between the treatment and placebo arms using Mixed Models. For the dose response analysis, the dose vs RAS activity will be plotted to explore the degree of modulation for each Ang peptide at the various doses.

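### Safety events after withdrawal are followed incompletely (2 months of calls after event-driven exits, none stated after others), so post-withdrawal counts depend on how many leave each arm and when

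*Combined protocol and SAP*

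**What the plan says.** All places are in the combined protocol and SAP.

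- Section 1: the primary objective is to "determine the safety and dose-response of target engagement" for candesartan. Section 5.1: "Participants will be treated for 1 year".
- Section 7.4: if an adverse event leads to the drug being stopped, the participant leaving, or both, "the participant will be followed for 2 months post-withdrawal with a monthly phone call". The next sentence adds an invitation to the final visit evaluation, but only "if the participant has been in the study more than 5 month post baseline evaluation". It does not say when that visit takes place. The section also lets the study physician arrange extra visits, calls or tests where needed.
- Section 8 is headed Intervention Discontinuation, but it opens its list with "The criteria for discontinuing a subject's participation include". The list includes adverse events that require the drug to be stopped, as well as the participant's own request, relocation and other personal reasons. No contact after these non-event exits is described there or elsewhere.
- Section 9.1: "The statistical analysis will follow the intention-to-treat approach", with a per-protocol analysis as well.
- Section 9.3, Table 2: group is the independent variable, and the safety outcomes end with "number of discontinuations of candesartan, AE, SAE, Deaths". The only comparative method given is mixed models for change in outcomes. No safety observation window, person-time denominator or time-to-event method is stated.
- Section 7.2 records problems reported during the study and does not say what that means for someone who has left.

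**The concern.** Followed as written, the plan observes participants for different lengths of time according to why and when they leave. Completers are observed for 12 months. Event-driven leavers are observed until exit plus 2 months, with a possible later visit if they pass the 5-month mark. Other leavers are observed until exit. The shortest windows belong to those who leave in the first 5 months, which include the whole of dose escalation.

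If exits were balanced in number and timing, this would cost information but not distort the comparison. They may not be. Section 8 ends participation for hypotension, raised creatinine and raised potassium, and Section 7.1 links dizziness, fainting, renal failure and hyperkalemia to candesartan. If one arm has more or earlier exits, fewer of its later adverse events, SAEs and deaths are recorded. With 36 per arm and no person-time denominator planned, a reader of the safety table could not see that this had happened. The yearly summary to the DSMB (Section 7.3) would carry the same unevenness.

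**Working it through.** **Inputs from the documents.** 72 participants, 1:1 allocation (Section 5.1), 12 months planned, 2-month tail after event-driven exits (Section 7.4). 72/2 = 36 per arm, which agrees with the 36 per group in Section 6.5. Full observation would be 36 × 12 = 432 person-months per arm. No power calculation, withdrawal rate or event rate is given, so there is no safety figure to reproduce.

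**Assumed inputs.** Share withdrawn p, month of exit t, and a constant event hazard equal in both arms. Each scenario treats all exits as one type, and no credit is given for the invited final visit.

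**Step 1. Unobserved months per leaver.**

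| Exit month | Event-driven (12 − t − 2) | Other (12 − t) |
|---|---|---|
| 1 | 9 | 11 |
| 3 | 7 | 9 |
| 6 | 4, unless a final visit is held at month 12 | 6 |

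**Step 2. Observed fraction per arm.** Fraction = [(1 − p) × 12 + p × min(12, t + tail)] / 12. With t = 2, a leaver is observed for 4 months with the tail and 2 months without it.

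| p | With tail | Without tail |
|---|---|---|
| 5% | 11.6/12 = 0.967 | 11.5/12 = 0.958 |
| 10% | 11.2/12 = 0.933 | 11.0/12 = 0.917 |
| 20% | 10.4/12 = 0.867 | 10.0/12 = 0.833 |
| 30% | 9.6/12 = 0.800 | 9.0/12 = 0.750 |

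**Step 3. Expected count ratio (arm with more exits : other arm).** At equal hazard this is the ratio of the fractions.

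| Withdrawal | With tail | Without tail |
|---|---|---|
| 10% v 5% | 0.97 | 0.96 |
| 20% v 10% | 0.93 | 0.91 |
| 30% v 10% | 0.86 | 0.82 |

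At 20% v 10% with the tail, the unobserved time is 432 × (1 − 0.867) = 57.6 v 432 × (1 − 0.933) = 28.8 person-months.

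**Step 4. Sensitivity to timing.** With 15% to 30% v 10% withdrawn and exits anywhere from month 1 to month 6, the ratio runs from 0.98 to 0.80. Equal withdrawal at equal times gives 1.00.

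**Step 5. Scale in participants.** Assume a true 12-month risk of 15% in both arms (36 × 0.15 = 5.4 participants). A person observed for m months has observed risk 1 − 0.85^(m/12).

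- 20% v 10%, exit at month 2, tail (m = 4, risk 0.0527): 36 × (0.80 × 0.15 + 0.20 × 0.0527) = 4.70 v 36 × (0.90 × 0.15 + 0.10 × 0.0527) = 5.05.
- 30% v 10%, exit at month 1, tail (m = 3, risk 0.0398): 11.7% v 13.9%, or 4.2 v 5.0.
- The same without the tail (m = 1, risk 0.0135): 10.9% v 13.6%, or 3.9 v 4.9.

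The gap between arms is about 0.35 in the moderate case and about 1 in the most extreme. For outcomes commoner than the assumed 15%, the absolute shortfall would be larger.

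**The case against.** The strongest reply is that exposure plus a fixed tail is a recognised window for safety, and that intention-to-treat in Section 9.1 does not by itself prescribe another. The harms most likely to be caused by the drug are largely those that lead to withdrawal, and they are recorded before observation shortens. The withdrawal rates above are invented, the constant-hazard model describes background events better than harms clustered around titration, and the shift is small. Section 7.4 also distinguishes stopping the intervention from leaving the study, offers a final visit to later leavers and allows discretionary contact.

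Most of this stands, and it limits the point. A reader might infer that events after early stopping are never seen, or that the whole safety comparison is biased toward no harm. The documents support neither. Event-driven leavers get 2 months of calls, and some are invited back. Hypotension, the creatinine and potassium limits, and discontinuations of candesartan are themselves Table 2 outcomes, so an excess of event-driven exits on candesartan would appear as harm. Nor do the documents show that candesartan will lose more participants than placebo.

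What the reply does not remove: the plan never declares an exposure-plus-tail window, gives non-event leavers no tail at all, and leaves the final visit optional, untimed and closed to anyone who exits in the first 5 months. Section 8 also blurs the distinction that Section 7.4 makes.

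**Conclusion.** The point holds for events after withdrawal only. Their ascertainment is incomplete and uneven by reason and time of exit, in a trial that names safety in its primary objective and plans intention-to-treat analysis over 1 year. If exits differ between arms, the arm with more or earlier exits has fewer such events counted. The ratios rest on assumed withdrawal shares, exit at month 2 and equal constant hazards; later exits, or final visits held at month 12, would shrink the effect. At an assumed 15% risk the shift is usually about one event or less per arm of 36. This is an improvement worth making because it is cheap and the data may not be recoverable later. It is not a flaw that invalidates the safety comparison.

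**What to change.** In Sections 7.4 and 8, separate stopping study drug from leaving the study. For every randomised participant who stops drug for any reason and has not withdrawn consent to contact, continue AE, SAE and vital-status contact by phone at the remaining scheduled visits through month 12 (from months 3, 6, 9 and 12). The criteria for stopping drug need not change. In Section 9.3, report the Table 2 safety events by arm in two windows, through month 12 and on drug plus 2 months, each with person-months at risk.

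With complete contact each arm would have 432 person-months before deaths, and the imbalance caused by withdrawal would disappear. Participants who refuse all contact will still be missing, and the person-months would show how much.

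The cost is at most four short calls per stopper and one more table. Section 6.12.2 already allows phone visits, though it ties them to pandemic restrictions, so the wording should be extended. The main downside is that off-drug events dilute attribution in the month-12 table, which is why the on-drug-plus-2-months table is kept beside it.
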